5.1.11. Adverse Events

Adverse events (AEs) will be collected and assessed throughout the study according to the Schedule of Visits and Assessments ([Section 1.3](#)). The Investigator is responsible for ensuring that all adverse events observed by the clinical staff or reported by the subject that occur after the first application of investigational product and treated and/or followed up for up to 30 days after end of treatment or until the symptoms or value(s) return to the subject's Baseline value, or acceptable levels, as judged by the Investigator, are recorded in the subject's medical record and the eCRF.

The Investigator is responsible for ensuring that all serious adverse events observed by the clinical staff or reported by the subject that occur after signing of the informed consent through 30 days after the last day of the application of the investigational product or the end of study (whichever is later) are recorded in the subject's medical record and are submitted per SAE reporting requirements ([Section 5.7.2](#)).

AEs (whether serious or non-serious) and clinically significant abnormal laboratory test value(s) will be evaluated by the Investigator and treated and/or followed up for up to 30 days after end of treatment or until the symptoms or value(s) return to the subject's Baseline value, or acceptable levels, as judged by the Investigator.

Refer to [Section 5.7](#) for further details on Adverse Events.

5.2. Efficacy Evaluations

Investigators will be trained in the administration of rating scales. A training certificate is issued upon successful completion of the training and will be valid for 12 months, unless compliance issues are identified that warrant retraining.

Note: Palms and soles may be treated with the IP in this study, but will not be counted towards IGA, PASI or BSA assessments.

5.2.1. Scalp (S-IGA) and Body (B-IGA) Investigator Global Assessments

Investigator Global Assessments (S-IGA and B-IGA) will be performed according to the Schedule of Visits and Assessments ([Section 1.3](#)). The S-IGAs should be completed prior to any other physician assessments. The B-IGA will be the second efficacy assessment performed at clinic visits (after the S-IGA).

The IGAs are static evaluations of qualitative overall psoriasis severity. The global assessment scales are ordinal scales with five severity grades (reported only in integers of 0 to 4). Each grade is defined by a distinct and clinically relevant morphologic description that minimizes inter-observer variability.

Every effort must be made for the same Evaluator to complete the S-IGA and B-IGA for the subject at every study visit, particularly for Baseline and Week 8.

5.2.1.1. Scalp - Investigator Global Assessment of Disease (S-IGA)

The Scalp-IGA (S-IGA) will be the first efficacy assessment performed at clinic visits. As with other efficacy assessments, the S-IGA should be performed prior to the application of any Investigational Product.

Scale	Grade	Description
0	Clear	Plaque thickening = no elevation or thickening over normal skin Scaling = no evidence of scaling Erythema = none (no residual red coloration but post-inflammatory hyperpigmentation may be present)
1	Almost Clear	Plaque thickening = none or possible thickening but difficult to ascertain if there is a slight elevation above normal skin level Scaling = none or residual surface drying and scaling Erythema = light pink coloration
2	Mild	Plaque thickening = slight but definite elevation Scaling = fine scales partially or mostly covering the lesions Erythema = light red coloration
3	Moderate	Plaque thickening = moderate elevation with rounded or sloped edges Scaling = most lesions at least partially covered Erythema = definite red coloration
4	Severe	Plaque thickening = marked or very marked elevation typically with hard or sharp edges Scaling = non-tenacious or thick tenacious scale, covering most or all of lesions Erythema = very bright red coloration; extreme red coloration; deep red coloration

5.2.1.2. Body - Investigator Global Assessment of Disease (B-IGA, i.e. non-scalp)

The Body-IGA (B-IGA) will be the second efficacy assessment performed at clinic visits (after the S-IGA). As with other efficacy assessments, the B-IGA should be performed prior to the application of any Investigational Product. In assessing B-IGA, the scalp, palms, and soles should not be considered.

Scale	Grade	Description
0	Clear	Plaque thickening = no elevation or thickening over normal skin Scaling = no evidence of scaling Erythema = none (no residual red coloration but post-inflammatory hyperpigmentation may be present)
1	Almost Clear	Plaque thickening = none or possible thickening but difficult to ascertain if there is a slight elevation above normal skin level Scaling = none or residual surface drying and scaling Erythema = light pink coloration
2	Mild	Plaque thickening = slight but definite elevation Scaling = fine scales partially or mostly covering the lesions Erythema = light red coloration
3	Moderate	Plaque thickening = moderate elevation with rounded or sloped edges Scaling = most lesions at least partially covered Erythema = definite red coloration
4	Severe	Plaque thickening = marked or very marked elevation typically with hard or sharp edges Scaling = non-tenacious or thick tenacious scale, covering most or all of lesions Erythema = very bright red coloration; extreme red coloration; deep red coloration

5.2.2. Extent of Scalp Involvement

The extent of scalp involvement assessments will be performed according to the Schedule of Visits and Assessments ([Section 1.3](#)).

The extent of scalp involvement will measure the extent of the scalp affected by psoriasis, expressed as the percentage of total scalp surface area. For this assessment, the subject's thumb approximates 1% of the total scalp surface area.

5.2.3. Body Surface Area (BSA)

The BSA assessments will be performed according to the Schedule of Visits and Assessments ([Section 1.3](#)).

The BSA affected by psoriasis will be determined by the subject's hand method, where the subject's hand (including fingers) surface area is assumed to equal 1% of body surface area. The

BSA assessment includes the scalp, but it does not include the palms and soles. The total scalp (ie, 100% of the total scalp surface area) can be considered to be approximately 4% BSA.

5.2.4. Psoriasis Scalp Severity Index (PSSI)

PSSI assessments will be performed at study visits according to the Schedule of Visits and Assessments ([Section 1.3](#)).

Every effort must be made for the same Evaluator to complete the PSSI for the subject at every study visit.

The PSSI is used for the measurement of severity of psoriasis.

PSSI combines the assessment of the severity of scalp lesions and the area of scalp affected into a single score in the range 0 (no disease) to 72 (maximal disease).

The extent of scalp affected is scored based on the following:

0. 0% of involved area
1. < 10% of involved area
2. 10–29% of involved area
3. 30–49% of involved area
4. 50–69% of involved area
5. 70–89% of involved area
6. 90–100% of involved area

The severity is estimated by three clinical signs: erythema ('E'; redness), induration ('T'; thickness) and desquamation ('S'; scaling). Severity parameters are measured on a scale of 0 to 4, from none to maximum severity possible:

0. absent
1. slight
2. moderate
3. severe
4. severest possible

To calculate the PSSI, the sum of the severity rating for the three main signs are multiplied with the numerical value of the area affected:

PSSI = Sum of scores for erythema, induration and desquamation x involved area (range 0–72)

5.2.5. Psoriasis Area and Severity Index (PASI)

Assessments will be performed as single assessments at each timepoint, from which PASI will be calculated.

PASI assessments will be performed at study visits according to the Schedule of Visits and Assessments ([Section 1.3](#)).

Every effort must be made for the same Evaluator to complete the PASI for the subject at every study visit.

Psoriasis Area and Severity Index (PASI) is used for the measurement of severity of psoriasis.

PASI combines the assessment of the severity of lesions and the area affected into a single score in the range 0 (no disease) to 72 (maximal disease).

The body is divided into four sections (head (h) (10% of a person's skin); arms (a) (20%); trunk (t) (30%); legs (l) (40%)). Each of these areas is scored by itself, and then the four scores are combined into the final PASI. For each section, the percent of area (A) of skin involved is estimated and then transformed into a grade from 0 to 6 (A):

0. 0% of involved area
1. < 10% of involved area
2. 10–29% of involved area
3. 30–49% of involved area
4. 50–69% of involved area
5. 70–89% of involved area
6. 90–100% of involved area

Note: Palms and soles may be treated with the IP in this study, but will not be counted towards IGA, PASI or BSA assessments.

Within each area, the severity is estimated by three clinical signs: erythema ('E'; redness), induration ('T'; thickness) and desquamation ('S'; scaling). Severity parameters are measured on a scale of 0 to 4, from none to maximum severity possible.

To calculate the PASI, the sum of the severity rating for the three main signs are multiplied with the numerical value of the area affected and with the various percentages of the four body areas. These values are then added to complete the formula as follows:

$$\text{PASI} = 0.1 (\text{Eh} + \text{Th} + \text{Sh}) \text{Ah} + 0.2 (\text{Ea} + \text{Ta} + \text{Sa}) \text{Aa} + 0.3 (\text{Et} + \text{Tt} + \text{St}) \text{At} + 0.4 (\text{El} + \text{Tl} + \text{Sl}) \text{Al}$$

5.2.6. Scalp Itch-NRS (SI-NRS)

The Scalp Itch-NRS is a single-item scale to assess the patient-reported severity of their symptom at the highest intensity of scalp itching over the past 24 hours. Scalp Itch-NRS will be determined by asking the subject's assessment of worst itching of the scalp over the past 24 hours. The scale is from '0' to '10' ('no scalp itch' to 'worst scalp itch imaginable'). Subjects will complete the Scalp Itch-NRS assessment (Wang 2019).

SI-NRS Assessment will be performed by subjects **daily** at home according to the Schedule of Visits and Assessments (Section 1.3) starting 7 days prior to the scheduled Baseline/Day 1 visit up to the Week 8/Day 57 visit.

The SI-NRS should be completed first and then WI-NRS.

SCALP ITCH NUMERIC RATING SCALE

Please rate the itching severity of your **scalp** due to your psoriasis by circling the number that best describes your **worst** level of itching in the **past 24 hours**.

[figure not shown]
0	1	2	3	4	5	6	7	8	9	10
0 = No scalp itch									10 = Worst scalp itch imaginable	

5.2.7. Worst Itch-Numerical Rating Scale (WI-NRS)

Given that itch is an important symptom of psoriasis, a WI-NRS assessment is included in the present study. The WI-NRS has been described as optimal for demonstrating a level of clinically meaningful improvement in itch severity in other skin conditions, including other forms of eczema (Yosipovitch 2019) and psoriasis (Kimball 2016).

WI-NRS Assessment will be performed by subjects **daily** at home according to the Schedule of Visits and Assessments ([Section 1.3](#)) starting 7 days prior to the scheduled Baseline/Day 1 visit up to the Week 8/Day 57 visit.

The WI-NRS has been developed as a simple, single item to assess the patient-reported severity of this symptom at its highest intensity during the previous 24-hour period. ([Naegeli 2015](#)). The WI-NRS will be determined by asking the subject's assessment of worst itch over the past 24 hours. The scale is from '0 to 10' ("no itch" to "worst imaginable itch"). Subjects will be asked on a scale of 0 to 10, with 0 being "no itch" and 10 being "worst itch imaginable", how would you rate your itch at the worst moment during the previous 24 hours?

5.2.8. Psoriasis Symptom Diary (PSD)

The PSD will be performed at study visits according to the Schedule of Visits and Assessments ([Section 1.3](#)). The PSD includes items related to Itching (question 1), Pain (question 9) and Scaling (question 11).

Only adult subjects will complete the PSD. See [Appendix 6](#) for the PSD.

5.2.9. Scalpdex

The Scalpdex ([Appendix 7](#)) will be performed by subjects according to the Schedule of Visits and Assessments ([Section 1.3](#)).

5.2.10. Dermatology Life Quality Index (DLQI) and Children's Dermatology Life Quality Index (CDLQI)

The DLQI (ages 17+ years) and CDLQI (ages 12-16 years, inclusive) will be performed according to the Schedule of Visits and Assessments ([Section 1.3](#)). The DLQI/CDLQI is a simple, self-administered and user-friendly validated questionnaire. The DLQI/CDLQI is designed to measure the health-related quality of life of patients suffering from a skin disease. The DLQI/CDLQI consists of 10 questions concerning patients' perception of the impact of skin diseases on different aspects of their health-related quality of life over the last week.

1. The DLQI ([Appendix 8](#)) will be completed by subjects ages 17 years and older. The CDLQI ([Appendix 9](#)) will be completed by caregivers of subjects ages 12-16 years. If a subject is 16 years old and turns 17 during the study, they will continue to complete the CDLQI.

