APPENDIX 9. CHILDREN'S DERMATOLOGY LIFE QUALITY INDEX (CDLQI)

Subject Number:
Age:

Diagnosis:
Date:

CDLQI
SCORE:

The aim of this questionnaire is to measure how much your skin problem has affected you OVER THE LAST WEEK. Please tick ✓ one box for each question.

1. Over the last week, how itchy , "scratchy", sore or painful has your skin been?	Very much 	Quite a lot 	Only a little 	Not at all 		
2. Over the last week, how embarrassed or self conscious , upset or sad have you been because of your skin?	Very much 	Quite a lot 	Only a little 	Not at all 		
3. Over the last week, how much has your skin affected your friendships ?	Very much 	Quite a lot 	Only a little 	Not at all 		
4. Over the last week, how much have you changed or worn different or special clothes/shoes because of your skin?	Very much 	Quite a lot 	Only a little 	Not at all 		
5. Over the last week, how much has your skin trouble affected going out , playing , or doing hobbies ?	Very much 	Quite a lot 	Only a little 	Not at all 		
6. Over the last week, how much have you avoided swimming or other sports because of your skin trouble?	Very much 	Quite a lot 	Only a little 	Not at all 		
7. Last week , was it school time ? 	If school time: Over the last week, how much did your skin problem affect your school work ?	Prevented school 	Very much 	Quite a lot 	Only a little 	Not at all 
OR						
was it holiday time ? 	If holiday time: How much over the last week, has your skin problem interfered with your enjoyment of the holiday ?	Very much 	Quite a lot 	Only a little 	Not at all 	

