- d. Height will be collected at Screening and Week 8. Weight will be collected at all study visits. Subjects should void prior to weight being taken and remove any objects of significant weight (i.e., jackets, outerwear, shoes, cell phones, wallet, key chains, etc.). A 5% unintentional weight loss from Baseline should be reported to the medical monitor.
- e. S-IGA will be a 5-point scale ranging from clear (0) to severe (4) and is evaluated for the scalp only. B-IGA will use the same scale as S-IGA but will evaluate the entire body (except the scalp, palms, and soles). PSSI is scored on a 0-72 scale and evaluates the scalp only. PASI assessment should exclude palms and soles. **S-IGA and B-IGA should be completed prior to other Investigator assessments and every effort should be made for the same evaluator to complete at each study visit.**
- f. Total BSA affected by scalp and body psoriasis will be determined by the subject's hand method, where the subject's hand (including fingers) surface area is assumed to equal 1% of body surface area. Scalp will be included in total BSA measurement, but palms and soles will be excluded. The total scalp (ie, 100% of the total scalp surface area) can be considered to be approximately 4% BSA.
- g. Extent of scalp involvement will be the extent of psoriasis involved, expressed as a percentage of total scalp.
- h. The DLQI will be completed by subjects ≥ 17 years of age. The CDLQI will be completed for subjects 12 to 16 years old, inclusive. Scalpdex will be completed by all subjects. PSD will be completed by subjects ≥ 18 years of age.
- i. Subjects/parents/caregivers will complete the SI-NRS and WI-NRS daily at home starting 7 days prior to the Baseline/Day 1 visit to Day 57 (Week 8) visit. Daily SI-NRS and WI-NRS will be completed in the evening prior to IP application (except at Baseline and Week 2 when IP is applied at the clinic). **The SI-NRS should be completed first and then WI-NRS.**
- j. Local tolerability assessments include both investigator and subject assessments. The Investigator assessment of skin irritation (Berger and Bowman skin irritation score) is to be recorded prior to IP application.

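### The documents conflict on who answers the CDLQI and the daily itch scores, and as written they permit proxy answers on self-report instruments without a constant or recorded respondent

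*Protocol*

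**What the plan says.** On the CDLQI, Protocol 5.2.10 states: "The DLQI/CDLQI is a simple, self-administered and user-friendly validated questionnaire". It describes the content as "10 questions concerning patients' perception of the impact of skin diseases". The numbered paragraph that follows says the CDLQI "will be completed by caregivers of subjects ages 12-16 years", and then: "If a subject is 16 years old and turns 17 during the study, they will continue to complete the CDLQI". The form in Appendix 9 opens: "The aim of this questionnaire is to measure how much your skin problem has affected you OVER THE LAST WEEK". SAP Table 1, footnote h, says: "The CDLQI will be completed for subjects 12 to 16 years old, inclusive".

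On itch, Protocol 5.2.6 says the SI-NRS "is a single-item scale to assess the patient-reported severity of their symptom" and that subjects complete it daily at home. Protocol 5.2.7 describes the WI-NRS in the same way. SAP Table 1, footnote i, reads: "Subjects/parents/caregivers will complete the SI-NRS and WI-NRS daily at home starting 7 days prior to the Baseline/Day 1 visit".

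SAP 6.1.3 places six SI-NRS endpoints and one WI-NRS endpoint among the secondary endpoints tested under alpha control. SAP 2.2.2.3 and Table 6 list the CDLQI among the other efficacy endpoints.

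**The concern.** A self-report scale completed by someone else measures that person's impression. A parent cannot directly observe a child's worst itch over the past 24 hours, and can only infer how embarrassed or upset the child felt. If the caregiver sentence is followed, the CDLQI results for those subjects are proxy scores on a form written for the child.

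For the itch scores the further risk is a change of respondent. A parent might make some or all of the entries before treatment and the adolescent those at follow-up, or the reverse. The difference between the two raters would then enter the change score as if it were a change in itch.

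The itch scores are where this matters. WI-NRS Success at Week 8 is the first test in Family 2. If it fails, sequential testing in that family stops and Family 1 is tested at 0.01 instead of 0.015. SI-NRS Success at Week 8 is the first test in Family 1.

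**Working it through.** The plan gives no figure to reproduce. The check sets the respondent rules side by side and counts the endpoints they reach.

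| Instrument | Place | Who answers |
|---|---|---|
| CDLQI | Protocol 5.2.10, description | The patient (self-administered, own perception) |
| CDLQI | Protocol 5.2.10, instruction | Caregiver, ages 12-16 |
| CDLQI | Protocol 5.2.10, rule on turning 17 | Reads most naturally as the subject |
| CDLQI | Protocol Appendix 9 | The child, addressed directly; no caregiver form shown |
| CDLQI | SAP Table 1, footnote h | Not named; completed for the subject |
| SI-NRS, WI-NRS | Protocol 5.2.6, 5.2.7 | The subject |
| SI-NRS, WI-NRS | SAP Table 1, footnote i | Subject, parent or caregiver; no age limit |

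**Safeguards.** The protocol asks for the same evaluator at every visit for the S-IGA, B-IGA, PSSI and PASI (5.2.1, 5.2.4, 5.2.5). The turning-17 rule keeps the CDLQI form constant. Neither provision covers the person answering. Nothing found in either document fixes the respondent for the CDLQI or the itch scores, records who answered, or uses that information in a derivation. When a day has two or more itch entries, SAP 6.1.7 takes the most severe, whoever made it.

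**Endpoint count (SAP 6.1.3).**
- Family 1 has 5 endpoints, Family 2 has 7 and Family 3 has 6: 5 + 7 + 6 = 18.
- SI-NRS supplies 5 in Family 1 and 1 in Family 3. WI-NRS supplies 1 in Family 2. Total: 5 + 1 + 1 = 7 of 18.
- Four of the seven use the 4-point responder threshold: SI-NRS at Weeks 8, 4 and 2, and WI-NRS at Week 8.
- Three are change scores: SI-NRS at Week 1, 72 hours and Day 1.

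**Where a change of respondent would act.** The Week 1, 2, 4 and 8 endpoints compare weekly averages, so an occasional entry by another person is diluted. The 72-hour and Day 1 endpoints compare one daily score (study day 4 or 2) with the last daily score before treatment (SAP 6.1.1, 6.1.7), so a single entry by another person passes undiluted into the difference. Their span is only a few days, however, so a drift of respondent between the baseline week and Week 8 does not reach them.

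**Size.** The effect depends on the number of subjects for whom a caregiver might answer and on the share of entries a caregiver made. The documents give the adolescent age range (12-17) but no count, and no share of entries. No magnitude can be derived.

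**The case against.** The strongest reply is that this is a drafting slip. The protocol text on itch is clear that subjects answer, SAP 8.2.1 again speaks of the subject's assessment, and SAP section 1 says it does not repeat operational aspects of data collection unless relevant to the analysis. The three-way wording in footnote i recurs in footnote p, about applying the product, so it may be generic household phrasing rather than permission for a parent to pick the score. The protocol's own footnote i cannot be read in the public text, so the itch conflict is visible only in the SAP. All of this stands and lowers the weight of the itch part. It does not remove the conflict: footnote i literally names parents and caregivers as completing the scores, and no other rule excludes them.

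Three stronger readings are tempting and are not supported:
- **That respondents are mixed within change scores by plan.** Nothing prescribes this. For the CDLQI, consistent caregiver completion would give the same type of respondent at every visit. For the itch scores, mixing is merely not prevented.
- **That all CDLQI data are proxy reports.** This rests on one sentence, which the next sentence blurs and SAP footnote h does not repeat. It covers ages 12-16 only; 17-year-olds complete the DLQI.
- **That 7 of 18 secondary endpoints are compromised.** Seven is the number that use the instruments. Only an unknown share of entries, from an unknown number of subjects, could be affected.

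**Conclusion.** The contradiction is real and the point is minor. Protocol 5.2.10 disagrees with itself and with Appendix 9 on who completes the CDLQI; SAP Table 1, footnote i, disagrees with Protocol 5.2.6 and 5.2.7 on who completes the itch scores. These are stated instructions rather than missing detail, and a site that follows them collects proxy answers on self-report instruments.

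The itch scores carry the consequence because they feed alpha-controlled endpoints, including two that open a testing sequence. The CDLQI is not formally tested, and neither co-primary endpoint uses these instruments.

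The expected effect is extra noise and a mis-measured construct in some subjects. A reader might infer bias in favour of one arm, but assignment is randomised and double blind, and nothing in the documents suggests that caregiver completion would differ by arm. This judgement assumes that the blind holds and that caregiver entries are a minority of itch entries; the documents do not allow the second assumption to be checked.

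**What to change.** - In Protocol 5.2.10, replace the instruction that the CDLQI "will be completed by caregivers of subjects ages 12-16 years" with one that subjects aged 12-16 complete it themselves.
- In SAP Table 1, footnote i, and in any matching protocol footnote, name subjects alone as completing the SI-NRS and WI-NRS.
- In both places, state that a caregiver may help with the form but may not choose the answer, and that any entry a caregiver nevertheless completes is recorded as such.

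The cost is two wording changes, a line in site training and a respondent field on the form. It asks nothing new of participants: adolescents already complete the modified PHQ-A (Protocol 5.1.8), and all subjects complete the Scalpdex (SAP Table 1, footnote h).

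SAP section 1 records database lock on 09-Sep-2022 and unblinding on 12-Sep-2022, so rewording cannot alter the data already collected. For those data, the study report should say who completed the CDLQI and the itch scores where this is known, and say so plainly where it is not.
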